**DATA COLLECTION**

Patients will be evaluated at baseline in the clinic. At 1 month after the injection an in-person clinic follow-up visit will occur. At this visit, concomitant medications, pain assessment, and outcomes will be assessed, as well as a physical exam and review of adverse events. Three, six and twelve months post injection, research staff will send an email/text to patients with a link to the surveys. If patients do not complete surveys within a week, research staff will follow up with a phone call to the patients inquiring about their knee(s) and instruct them to complete the various assessment tools online (VAS, SANE, PFCAT, and KOOS). Research staff may call patients after they complete surveys to clarify any responses. Information about repeat injections will be collected, including date of injection. Additional visits, which include a physical exam, review of concomitant medications and adverse events, will be done as needed.

Medical history, concomitant medications and physical exam will be collected at the baseline visit, prior to randomization. Concomitant medications will also be collected at the following time points: 1, 3, 6 and 12 months. Adverse events will also be collected at all follow-up time points (1 day, 2 days, 1 month, 3 months, 6 months and 12 months after baseline).

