**Study Enrollment Staggering**

In order to help ensure patient safety and to help limit unreasonable risk the first six subjects will be enrolled in staggered intervals. One subject may be enrolled per week for the first six subjects. Half of the six subjects will be randomized to pAF and the other half will be randomized to SOC steroid. Preliminary safety data for the first six subjects will be gathered and reviewed by the Data Safety and Monitoring Board (DSMB). If the DSMB expresses no concern over the preliminary data, the study may proceed with enrollment.

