**A Phase I/II Randomized, Double-Blinded Standard of Care (Corticosteroid vs Sterile Amniotic Fluid for Osteoarthritis**

**PI: [name].**

**Version: 5.00 dated 23MAY2023**

point if new or worsening AEs arise. The subject reserves the right to come back into clinic for an in-person visit per standard of care.

- **48 hours:** Follow up phone call will be made 2 days after study drug injection. The phone call will be made to assess AEs. The study team will instruct the subject to contact the study team at any point if new or worsening AEs arise. The subject reserves the right to come back into clinic for an in-person visit per standard of care.
- **1 month:** Follow up in-person clinic visit with associated physical exam and questionnaires. This visit is part standard of care. If the patient is unable to return to clinic, the patient may receive a phone call by the study team to do remote clinic visit and complete questionnaires.
- **3 Months:** Patient questionnaires sent by mail or email/text. If the patient is non-responsive to initial contact additional follow up contact (e.g. additional email/phone calls/text) will be made by the study team. The patient may receive additional follow up contact (e.g. email/phone call/text) by the study team to clarify any responses. The study team will instruct the subject to contact the study team at any point if new or worsening AEs arise. The subject reserves the right to come back into clinic for an in-person visit per standard of care. This is a study related follow up.
- **6 Months:** Patient questionnaires sent by mail or email/text. If the patient is non-responsive to initial contact additional follow up contact (e.g. additional email/phone calls/text) will be made by the study team. The patient may receive additional follow up contact (e.g. email/phone call/text) by the study team to clarify any responses. The study team will instruct the subject to contact the study team at any point if new or worsening AEs arise. The subject reserves the right to come back into clinic for an in-person visit per standard of care. This is a study related follow up.

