- **12 Months:** Patient questionnaires sent by mail or email. If the patient is non-responsive to initial contact additional follow up contact (e.g. additional email/phone calls/text) will be made by the study team. The patient may receive additional follow up contact (e.g. email/phone call/text) by the study team to clarify any responses. The study team will instruct the subject to contact the study team at any point if new or worsening AEs arise. The subject reserves the right to come back into clinic for an in-person visit per standard of care. This is a study related follow up.

The patient may also receive additional phone calls by the study team to assess any adverse events that occur in between the scheduled 1-month follow-up visit and subsequent emails, phone calls, and/or text messages.

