**A Phase I/II Randomized, Double-Blinded Standard of Care (Corticosteroid vs Sterile Amniotic Fluid for Osteoarthritis)**

**PI: [name].**

**Version: 5.00 dated 23MAY2023**

**PATIENT STUDY CALENDAR**

	Screening /Baseline	Day 1 (24± 5 hours post injection)	Day 2 (48 ± 5 hours post injection)	1-Month (± 1 week)	3-Months (± 2 weeks)	6-Months (± 1 month)	12-Months (± 1 month)	As needed
Eligibility A	X							
Informed Consent	X							
Medical History	X							
Concomitant Medications	X			X	X	X	X	X
Physical Exam	X			X				X
Laboratory tests B	x							
Randomization	X							
Study Drug Administration	X							
Follow-up Contact C		X	X	X D	X	X	X	X
In Person Follow-up Visit				X D				X
Pain Assessment E	X			X	X	X	X	
Outcome Assessment F	X			X	X	X	X	
Review of systems questionnaire G					X	X	X	
Review of adverse events H		X	X	X	X	X	X	X
Knee Aspiration I	X							
Aspiration Characteristics J	X							

B Laboratory tests include: PT/INR (only applicable to patients taking blood thinners) and urine hCG (only applicable to women of childbearing potential)

C Follow up Email/phone call/text may occur to clarify any responses and/ or assess AEs and/ or establish contact with the patient.

D The patient may receive a phone call by the study team to do remote clinic visit and complete questionnaires if the patient is unable to return to clinic to do in-person visit.

E Visual Analog Scale (VAS).

F Single Assessment Numerical Evaluation (SANE), PROMIS Physical Function CAT (PF CAT), and Knee Injury and Osteoarthritis Outcome Scale (KOOS). These surveys may be sent via email/text or done over the phone.

G This questionnaire may be sent via email/text or done over the phone.

H The study team may call the participant to assess adverse events in between the scheduled follow-up visit and phone calls.

I If deemed applicable by the treating provider.

J Only applicable if there is a suspicion of infection as determined by the treating provider.

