**STUDY STOPPING/ DISCONTINUATION**

Events used to trigger discontinuation or stopping of the study pending a safety investigation include:

- If there is one death, irrespective of attribution
- If there is a SAE, that is possibly or probably related to study drug injection (pAf or steroid injection)
- Signs of severe hypersensitivity in a least 10% of enrolled patients
- If there is one case of hypersensitivity, defined as an acute inflammatory reaction requiring invasive intervention
- If there an adverse event that is classified as Severe per protocol that is possibly or probably related to the IP Injection (AF or steroid)

In the event study enrollment has been suspended due to the above criteria or any other reason the FDA, the DSMB, IRB and the Sponsor must be notified. Enrollment and treatment will be resumed after a review of the incident and of any corrective and preventive actions have been established with consultation between the study team, the Sponsor, and the DMSB. The study may not resume without FDA approval.

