**A Phase I/II Randomized, Double-Blinded Standard of Care (Corticosteroid vs Sterile Amniotic Fluid for Osteoarthritis**

**PI: [name].**

**Version: 5.00 dated 23MAY2023**

- **Not Related:** The event is clearly related to other factors, such as the subject's clinical state, therapeutic interventions, or concomitant drugs administered to the subject.
- **Possibly Related:** The event follows compatible temporal sequence from the time of beginning the assigned study intervention, but could have been produced by other factors such as the subject's clinical state, therapeutic interventions, or concomitant drugs administered to the subject.
- **Probably Related:** The event follows a reasonable temporal sequence from the time of beginning the assigned study intervention, and cannot be reasonably explained by other factors such as the subject's clinical state, therapeutic interventions, or concomitant drugs administered to the subject.

**Severity:** The severity, which is a measure of intensity, of clinical adverse events and laboratory abnormalities will be recorded by the site investigator and categorized. The following guidelines will be used to describe severity.

- **Mild:** The event requires minimal or no treatment and does not interfere with the participants daily activities.
- **Moderate:** The event results in a low level of inconvenience or concern with the therapeutic measures. Moderate events may cause some interference with functioning.
- **Severe:** The event interrupts a participant's usual daily activity and may require systemic drug therapy or other treatment. Severe events are usually potentially life-threatening or incapacitating. Of note, the term "severe" does not necessarily equate to "serious".

**Expectedness of the Event:** All adverse events, including serious adverse events, will be evaluated as to whether their occurrence was expected or unexpected. An AE will be considered unexpected if the nature, severity, or frequency of the event is not consistent with the risk information described for the study intervention.

- **Expected:** An event is considered expected if it is known to be associated with the underlying condition or is related to the study intervention and is mentioned in the protocol, informed consent, or other study documents. An event may be expected despite the study subject's clinical state immediately prior to the event.

Expected adverse events for this study are:

- Pain at injection site

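### The first-six safety stagger is counted from randomisation, so it guarantees no interval between injections and no adverse-event review of one subject before the next is injected

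*Combined protocol and SAP*

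**What the plan says.** The Study Enrollment Staggering section gives patient safety as its reason and sets the pace: "One subject may be enrolled per week for the first six subjects". Three of the six go to each arm. The DSMB then reviews the six together before enrolment continues; no minimum follow-up for that review is given.

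The Randomization section counts a patient as enrolled from randomisation, dosed or not. It lets randomisation happen when the patient is first seen or on the injection day. Under Study Drug Administration, all injections are given at the Orthopedic Center, so patients consented at other clinics must travel there.

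On AE review, Data Collection states, with times counted from baseline: "Adverse events will also be collected at all follow-up time points (1 day, 2 days, 1 month, 3 months, 6 months and 12 months". The Patient Study Calendar places the day 2 contact at 48 ± 5 hours and the 1-month contact within ± 1 week. Between these two there is optional or patient-led cover:

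- Footnote H of the calendar: "The study team may call the participant to assess adverse events in between the scheduled follow-up visit and phone calls".
- The follow-up section, at both the 24-hour and the 48-hour call: "The study team will instruct the subject to contact the study team at any point if new or worsening AEs arise".
- Patients may come to clinic whenever they have pain or side effects, and as-needed visits include AE review.

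The further calls mentioned at the end of the follow-up section are for the time "in between the scheduled 1-month follow-up visit and subsequent emails, phone calls, and/or text messages", so they do not reach into the first month.

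Study Stopping/Discontinuation names this trigger: "If there an adverse event that is classified as Severe per protocol that is possibly or probably related to the IP Injection". The severity grading defines Severe: "The event interrupts a participant's usual daily activity and may require systemic drug therapy or other treatment". It then adds: "Severe events are usually potentially life-threatening or incapacitating".

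**The concern.** A stagger protects patients by letting an early reaction in one subject show before the next is exposed. The exposure is the injection, but the weekly limit is written on randomisation. If the two events are separated by a delay that varies between subjects, weekly randomisation need not give weekly injections. Nor does any sentence make an injection wait for the previous subject's AE calls. The DSMB sees the first six only as a group, so until then subjects 2 to 6 depend on the 24- and 48-hour calls and on self-report, and even those calls need not be finished before the next injection.

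The gap in scheduled AE review after 48 hours adds to this. Safety is the first primary objective, and one related Severe AE in either arm should pause the trial. That rule acts only on events the team knows about. An event that starts after 48 hours, is managed at home and is not volunteered would first be asked about at the 1-month contact, and dosing could continue until then.

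**Working it through.** The only figure in the plan that enters here is accrual (Sample Size Calculations): 60 patients at 5 randomisations per week is 60 / 5 = 12 weeks, which agrees with the stated 3 months or so. The plan gives no delay from randomisation to injection and no length for a month. I take a month as 30 days, one per week as exactly 7 days apart, and day 0 as the injection.

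**1. Spacing of injections in the first six.** If L is a subject's delay from randomisation to injection, the interval between two successive injections is 7 + (L of the later subject − L of the earlier subject).

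- Equal delays, including randomisation on the injection day for both: 7 days. Both early calls of the earlier subject then fall due about 5 days before the next injection.
- Earlier subject waits 5 days, later subject waits 0: 7 − 5 = 2 days. The 48-hour call may not be done.
- Earlier subject waits 7 days, later subject waits 0: 7 − 7 = 0 days.

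The text allows all three.

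**2. Gap in scheduled AE review.** The 1-month contact falls on day 30 ± 7, that is day 23 to 37. Subtracting day 2 gives 21 to 35 days. A 28-day month gives 19 to 33, a 31-day month 22 to 36. The ± 5 hours moves this by about 0.2 day.

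**3. What the gap means during the stagger.** Assume weekly injections on days 0, 7, 14, 21, 28 and 35, and an unvolunteered event in subject 1.

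| Onset just after | Wait until asked (days) | Further subjects injected |
|---|---|---|
| day 2 | 21 to 35 | 3 to 5 |
| day 7 | 16 to 30 | 2 to 4 |
| day 21 | 2 to 16 | 0 to 2 |

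If a day-7 call had to precede the next injection, events from days 2 to 7 would wait at most 5 days and no further subject would be injected first. Events after day 7 would still wait as in the second row.

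**4. What the gap means after the DSMB review.** At 5 per week, an event just after day 2 is followed by 21 × 5/7 = 15 to 35 × 5/7 = 25 randomisations. If onset is uniform over the gap (my assumption):

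- As planned, the mean wait is 21/2 = 10.5 to 35/2 = 17.5 days, or 7.5 to 12.5 randomisations.
- With a day-7 call it is (5²/2 + 16²/2)/21 = 6.7 to (5²/2 + 30²/2)/35 = 13.2 days, or 4.8 to 9.4 randomisations.
- The saving is 2.7 to 3.1 randomisations per such event.

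**The case against.** A reader might infer that the stagger does not space injections at all. The documents do not support that. Randomisation on the injection day is allowed, and the Patient Study Calendar puts randomisation and drug administration in one Screening/Baseline column. Data Collection dates AE reviews from baseline while the calendar dates days 1 and 2 from injection, which suggests that the two usually coincide. On that path injections fall about weekly and both early calls come due before the next one. The 0-day interval is a literal worst case. What stands is that spacing is not guaranteed, and that even on the weekly path no injection depends on a completed call.

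A reader might also infer that AEs in the first month would be missed. They would still be asked about at 1 month, and optional calls, as-needed visits and two instructions to self-report come earlier. The uncovered event is narrow: Severe, related, later than 48 hours, managed at home and unreported. Events that threaten life or incapacitate are the least likely to stay silent, and a milder flare could be graded Moderate. This limits the concern to delay. It does not remove it, because the Severe definition also takes in an event that interrupts daily activity, and none of the cover is a mandatory question from staff.

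The 15 to 25 might be read as patients exposed. They are randomisations, not necessarily injections, conditional on an event for which the documents give no probability. A suspension halts treatment as well as enrolment, so it would also protect patients randomised but not yet injected.

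Finally, subject 6 would enter about day 35, when subject 1 is at or near the 1-month contact, and the DSMB must then raise no concern. That is real protection for later patients, but it does not space the first six. With weekly injections and a review on day 37, just after subject 6's 48-hour call, subjects 3 to 6 would not have reached a nominal day-30 visit. The manual of operations or the DSMB charter may add procedures; they are not in the documents.

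**Conclusion.** The point holds in a limited form. As written, the stagger guarantees neither a minimum interval between injections in the first six nor an AE review of one subject before the next is injected. That follows from the text alone. How far actual injections would depart from weekly depends on a delay that the protocol does not state: the interval is 7 days with equal delays and 0 days if they differ by 7.

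The secondary point, 21 to 35 days without a scheduled AE review after 48 hours, rests on a 30-day month (19 to 36 days across months of 28 to 31 days). The consequence is possible delay in detecting a stopping event. The patient counts are conditional illustrations, and the averages also need the uniform-onset assumption. This is a minor safety improvement at low cost. It does not affect the validity of the planned analysis.

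**What to change.** Main change, in Study Enrollment Staggering: count the stagger from injection, with at least 7 days between injections for the first six subjects. Require the previous subject's 24-hour and 48-hour AE reviews, plus an AE call at about day 7, to be completed before the next injection.

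Secondary change: make one of the optional calls in calendar footnote H mandatory at about day 7 for every patient. Add day 7 to the Patient Study Calendar, to Data Collection and to the AE time frames under Exploratory Endpoints.

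Cost: one short call for each of 60 patients, about 60 calls by existing staff, and a calendar edit. If calls are on time, six injections take 5 × 7 = 35 days, the same as weekly injections now; a late call could add a few days. The day-7 call shortens the gap without closing it, since events after day 7 could still wait up to 16 to 30 days for the 1-month contact. Day 7 is a practical choice that matches the weekly stagger; the protocol does not dictate it.

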**A Phase I/II Randomized, Double-Blinded Standard of Care (Corticosteroid vs Sterile Amniotic Fluid for Osteoarthritis**

**PI: [name].**

**Version: 5.00 dated 23MAY2023**

At the end of 12 months, the pain and outcomes assessments for both treatment arms will be compared and assessed using the Visual Analog Scale (VAS), Single Assessment Numerical Evaluation (SANE), PROMIS Physical Function CAT (PF CAT), and Knee Injury and Osteoarthritis Outcome Score (KOOS).

**DATA ANALYSIS**

The primary endpoint (need for a repeat injection) will be compared between the two arms using Fisher's Exact test. An alpha 0.05 will be used as the threshold for statistical significance. Missing data will remain missing rather than be imputed since this is a pilot study assessing preliminary safety and feasibility.

The secondary endpoint (pain) will consist of a comparison of mean values for VAS scoring scales pre-injection and at follow-up visits at 1, 3, 6 and 12-months. Clinically significant outcomes will be determined based on the minimal clinically important difference (MCID) occurring for each respective scale, which is defined as the smallest change score needed for the effect to be considered clinically relevant.

Continuous secondary and exploratory endpoints will be compared between arms using Wilcoxon Rank Sum tests. Categorical endpoints (including safety outcomes) will be compared between arms using Chi-squared tests. In cases of small counts, exact tests may be used.

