**OUTCOMES OF THE STUDY**

### **Primary Endpoint**

- The need for a repeat allogeneic intra-articular injection [Time Frame: 6 months].

Participants in both the SOC and pAF treatment arms may require and/or request rescue medication (i.e. SOC injection) at any time and will be given per PI discretion as part of standard of care. The clinicians will not know which study arm the study participant is in but will treat the participant with the SOC injection. This information will be documented and collected in the Electronic Medical Record (EMR), as well as the study's electronic data capture system. Participants will not be given any additional pAF injections throughout the 12-month study period.

The participant will continue to be treated with SOC injections as needed. The outcome will be an indicator of whether or not a subject received a rescue medication within 6 months. Sensitivity analyses will also be performed to assess the number of rescue medications given over the course of a year.

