**Randomization**

Consented patients will be randomized into two groups at a 1:1 ratio using block permutations of 2 and 4. Randomization will be done using either an online randomization service or envelope system. Randomization will occur following the patient's consent into the study, either at the initial visit or the day of the planned injection. Once the randomization number is obtained, unblinded research staff will prepare the appropriate study drug. The injections will be blinded to the research coordinator in charge of data entry, the treating physician and the patient. Clinical staff will prepare the study drug injection and maintain the blind by placing a blank label over the syringe to ensure that the treatment is blinded to the patient and treating physician. Once a patient has been randomized, they become an enrolled subject and will be included in the intention to treat analysis of the trial outcomes, regardless of whether or not they receive study drug.

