**A Phase I/II Randomized, Double-Blinded Standard of Care (Corticosteroid vs Sterile Amniotic Fluid for Osteoarthritis**

**PI: [name].**

**Version: 5.00 dated 23MAY2023**

**WITHDRAWAL FROM STUDY**

A patient may withdraw from the study at any time, without a penalty or loss of benefits. Data collected up until the point of withdrawal will be still be used in efficacy and safety analyses.

Patients should not be withdrawn from the trial for AEs. Patients who discontinue the study will be followed for safety according to the safety monitoring plan and attempts to complete all safety assessments will be made, unless the subject withdraws consent.

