**SAMPLE SIZE CALCULATIONS AND STATISTICAL POWER**

The primary endpoint is the need for a repeat injection. Based on historic data, about 50% of individuals who receive a steroid injection return for an additional injection within six months due to pain. Assuming a significance level of 0.05 and a need for a repeat injection in the AF arm of 10%, with 60 total patients (30 per arm), we have about 90% power to detect a difference in need for repeat injections at 6 months between the two arms. Expecting approximately 5 randomizations per week, 60 patients will take approximately 3 months to enroll.

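### The primary Fisher comparison has no rule for participants lost before 6 months without a recorded rescue, no missing-data sensitivity analysis, and no allowance for loss in its power figure.

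*Combined protocol and SAP*

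**What the plan says.** The Primary Endpoint section defines a binary variable: "The outcome will be an indicator of whether or not a subject received a rescue medication within 6 months". Rescue injections are to be recorded in both the medical record and the study database. Data Analysis states that this endpoint "will be compared between the two arms using Fisher's Exact test" at alpha 0.05, and on missing values says only: "Missing data will remain missing rather than be imputed since this is a pilot study assessing preliminary safety and feasibility".

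Three other passages bear on who is counted:

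- Randomization: every randomised subject "will be included in the intention to treat analysis of the trial outcomes, regardless of whether or not they receive study drug".
- Withdrawal from Study: "Data collected up until the point of withdrawal will be still be used in efficacy and safety analyses".
- Data Collection: "Information about repeat injections will be collected, including date of injection".

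The sample size section states that, "with 60 total patients (30 per arm), we have about 90% power to detect a difference", for assumed 6-month rates of 50% (steroid) and 10% (pAF). It names no loss rate. The only sensitivity analysis named for the primary endpoint counts rescue medications over a year and does not deal with missing status.

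**The concern.** A 2x2 table needs a yes or a no for each person. Take a participant who withdraws event-free at month 3 and whose later status cannot be established. The intention-to-treat sentence keeps this person in. The withdrawal sentence says the three event-free months are used, but a binary indicator cannot use them. The no-imputation sentence, combined with Fisher's test, takes the person out. A participant who had a rescue at month 2 and withdrew at month 3 has a known outcome and stays. Events are thus retained and event-free losses removed, which affects both the rates and the denominators.

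Unknown status is foreseeable. After month 1, scheduled follow-up is by mail, email, text or phone, and the visit descriptions themselves plan for non-response. The pilot rationale for not imputing carries little weight for this endpoint, because the plan attaches a formal 0.05 test and a power claim to it. The stakes are a primary estimate, and possibly a significance call, that depend on a classification rule nobody has written down.

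**Working it through.** **Inputs.** From the documents: 30 per arm, 50% vs 10%, alpha 0.05, Fisher's exact test. Assumed, because the documents give nothing: a two-sided test, loss of 10% or 20%, equal loss in both arms and, for step 3, constant hazards.

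**1. The stated power.** Power is the sum, over all tables (a, b) with two-sided Fisher p of at most 0.05, of Bin(a; n, 0.5) x Bin(b; n, 0.1). At n = 30 this gives 0.9135. The plan's figure of about 90% reproduces.

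**2. Power with fewer evaluable participants, rates held at 50% vs 10%.**

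| Evaluable per arm | Missing | Power |
|---|---|---|
| 30 | 0% | 0.9135 |
| 29 | 3% | 0.9002 |
| 28 | 7% | 0.8906 |
| 27 | 10% | 0.8725 |
| 24 | 20% | 0.8342 |
| 23 | 23% | 0.8114 |
| 21 | 30% | 0.7585 |

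**3. Rates when pre-loss rescues are kept and event-free losses excluded.** Let p be the true 6-month rate and d the 6-month loss probability, with loss independent of rescue. Put L = -ln(1-p), M = -ln(1-d) and T = L + M.

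- Rescue seen before loss: E = (L/T)(1 - exp(-T))
- Event-free and still followed at 6 months: C = exp(-T) = (1-p)(1-d)
- Rate in the test: E/(E + C)

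At d = 0.20:

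- Steroid: L = 0.693, M = 0.223, T = 0.916, so E = 0.454 and C = 0.400. The rate is 0.454/0.854 = 53.2%.
- pAF: L = 0.105, T = 0.329, so E = 0.090 and C = 0.720. The rate is 0.090/0.810 = 11.1%.

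At d = 0.10 the same steps give 0.477/0.927 = 51.5% and 0.095/0.905 = 10.5%. The difference between arms widens from 40 points to 41.0 and 42.1. With rounded expected arm sizes (28 and 27; 26 and 24), power is about 0.91 and 0.90.

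**4. The same losses counted as no rescue.** The rate is then E over everyone randomised: 47.7% vs 9.5% at 10% loss (power 0.893) and 45.4% vs 9.0% at 20% loss (power 0.868). At 20% loss the steroid rate moves by 53.2 - 45.4 = 7.8 points on the choice of rule alone.

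**5. Outcome-related loss, all lost participants excluded.** The completer rate is (0.5 - dq)/(1 - d), where q is the rescue rate among those lost. For the steroid arm at d = 0.20:

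- q = 0.75 gives 0.35/0.80, or about 43.7%.
- q = 0.50 gives 50%.
- q = 0.25 gives 0.45/0.80, or about 56.2%.

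**6. Can the rule change the conclusion?** Illustrative counts with 3 unknown per arm, two-sided Fisher:

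- 12 vs 3 rescues: complete case 12/27 vs 3/27, p = 0.014. Worst case for pAF, with its unknowns counted as rescued and the steroid unknowns as not: 12/30 vs 6/30, p = 0.16.
- 14 vs 6 rescues: complete case 14/27 vs 6/27, p = 0.047. Unknowns counted as no rescue: 14/30 vs 6/30, p = 0.054.

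**The case against.** The strongest reply is that the plan leaves a case unspecified and that stronger conclusions go beyond the text. Four such readings are tempting.

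- A reader might infer that everyone who misses the 6-month survey is dropped. The documents do not say so. The outcome can come from the medical record, repeat contact is planned, and a rescue before withdrawal is kept. Only participants whose status remains unknown are affected.
- A reader might infer that the intention-to-treat rule is contradicted outright. That sentence concerns inclusion whether or not study drug is received, and does not speak to missing outcomes.
- A reader might infer that the rates must be biased upward. That needs early rescues to be kept and event-free losses excluded. If all losses are excluded and loss is unrelated to outcome there is no bias, and step 5 shows that the bias can also run downward.
- A reader might infer that the stated power is lost. It stays above 80% down to 23 evaluable per arm. In the upward-bias scenario it barely moves, because the difference widens. A simulation with 20% of event-free participants missing and every event seen gave power of 0.91 and type I error of 0.024 to 0.033.

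All four limits stand. So does a caution about the remedy: Kaplan-Meier does not cure outcome-dependent ascertainment. In that same scenario, complete-case rates are 55.6% and 12.2%. Censoring event-free losses at a last contact at month 1 still gives 55.0% and 11.8%, and at month 3 gives 53.5% and 11.1%. That argues against making a log-rank test primary on these grounds.

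The reply does not supply the missing rule. No passage says that a record without a rescue counts as a no, or what to do with someone lost event-free.

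**Conclusion.** The point holds as a gap in the primary analysis. Read together, the endpoint definition, the withdrawal rule and the no-imputation rule exclude event-free participants of unknown status and retain those with an early rescue. This is in tension with analysing all randomised subjects, and nothing planned would show how much it matters.

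The effect on the rates is modest under independent loss: up to about 1.5 points at 10% loss and 3.2 points at 20%, both in the steroid arm. Its direction cannot be known if loss depends on outcome. The power figure is correct for 60 evaluable participants and is eroded by loss, by about 4 points at 10% missing and 8 points at 20% if the rates hold. The larger risk is that, with 30 per arm, a few unknowns can decide significance, as in step 6.

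These sizes rest on assumed loss rates, equal loss by arm, a two-sided test and, for the bias figures, constant hazards. None of these is in the documents.

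**What to change.** Keep Fisher's exact test as the primary analysis and, before unblinding, add the following to Data Analysis:

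- Rescue status to 6 months is ascertained for every randomised participant from the medical record and study contacts, whether or not the 6-month questionnaire is returned.
- A stated rule says when a record without a rescue counts as a no, and how a status that remains unknown is classified in the primary test.
- Best-case and worst-case bounds are reported for participants of unknown status.
- A supportive Kaplan-Meier 6-month risk is given by arm, with a risk difference and 95% CI. It uses the injection dates already collected and censors at withdrawal or last confirmed ascertainment. This makes use of partial follow-up, as the withdrawal section promises.

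In the sample size section, set power for a range of loss rates beside the 60-evaluable figure: about 91% with none missing, 87% with 10% and 83% with 20%.

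The cost is a few sentences, a little more analysis and a slightly less favourable power statement. No new data item is needed, although checking records for every participant takes some staff time. Kaplan-Meier assumes uninformative censoring, so the bounds must be reported with it.
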